1. INTRODUCTION

1.1. Background

Promacta® (Eltrombopag) received accelerated FDA approval on Nov 20, 2008 for the treatment of thrombocytopenia in patients with chronic immune (idiopathic) thrombocytopenic purpura (ITP) who have had an insufficient response to corticosteroids, immunoglobulins, or splenectomy. Formerly GlaxoSmithKline (GSK) and now Novartis is also developing eltrombopag for the treatment of aplastic anemia, MDS, and chemotherapy-induced thrombocytopenia.

Wiskott Aldrich Syndrome (WAS) is an X-linked disease characterized by immunodeficiency, eczema and thrombocytopenia; a milder form of the disease known as X-Linked Thrombocytopenia (XLT) also exists. The two forms are on a spectrum but typically patients with XLT may be relatively asymptomatic except for signs of bruising and bleeding whereas patients with full blown WAS manifest more symptoms making clinical distinction relatively easy. The estimated incidence in the US is 1 per million people (Sullivan et al. 1994 and Ochs and Rosen 2007). The thrombocytopenia in both WAS and XLT is characterized by: severe thrombocytopenia with platelet counts frequently less than 10-30,000/ul; small platelets which may be dysfunctional; and, as a result, a high rate of serious bleeding including intracranial hemorrhage. Currently patients are treated using platelet transfusion, splenectomy, and/or human stem cell transplantation (HSCT) and experimentally with gene therapy. These are effective in different ways but there appears to be a clearly increased risk of sepsis after splenectomy and morbidity and mortality with HSCT. In addition, even patients with full blown WAS who will undergo transplantation may benefit from waiting until they are 12-24 months of age instead of being transplanted at 2-6 months of age because of relentless thrombocytopenia. There is an estimated 10% risk of malignancy, e.g. development of lymphoma, but this is not usually an early phenomenon. Perhaps 1-3 of the 15 patients in the study might be at risk for lymphoma over a lifetime but it is not likely to happen during the relatively short time course of the study. If it were to happen in one patient, it would be attributed to the natural history of the disease. There would be no specific way to determine the etiology of any lymphoma that developed.

Because eltrombopag has been shown to be efficacious in substantially increasing platelet counts in a high percentage of adult and now pediatric chronic ITP patients, this study seeks to effectively treat patients who exhibit similar pathologies, as well as to evaluate the state of platelets in patients with WAS and relate it to clinical bleeding. Eltrombopag has recently been licensed for children over the age of 1 year for treatment of chronic ITP which is pertinent because the great majority of patients anticipated to be enrolled on this study are children. The study also aims to demonstrate whether eltrombopag administered daily will increase platelet production and platelet count and reduce bleeding in patients with WAS.

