- (4) ALT levels are ≥ 5 times ULN.
- If a subject has an adverse experience that would, in the investigator's judgment, make continued participation in the study an unacceptable risk
- Note: If the subject's ALT and bilirubin levels decrease so that both are < 1.5 times ULN, the

investigator may decide to restart the medication and monitor on a weekly basis.

- Study medications will be discontinued in the event of any thrombosis

If subject’s platelet count goes above 200,000, the dose of study medication will be reduced.

As indicated on page 5, perhaps 2-3 of the 15 patients in the study might be at risk over a lifetime for a malignancy such as lymphoma, but it is not very likely to happen during the relatively short time course of the study. If 1 patient develops another type of malignancy or 2 patients develop a Non-Hodgkin Lymphoma during the course of the study, the study will be stopped. Prior to the study being restarted (if this is the desire of the investigators), there will be a formal request to re-open the study submitted to the FDA with a letter of support from Novartis.

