6.3. Safety

This protocol is investigator initiated. The Principal Investigator is responsible for the study and will monitor the safety of the patients on the protocol.

The following safety will be reviewed by the Principal Investigator:

- Physical Exam
- Vital Signs
- Laboratory results (blood count, liver function tests, reticulocyte count, urine tests)
- SAE and AE events
- Bone marrow aspirations/biopsies (if relevant)

Adverse Events (AEs) will be graded according to Common Terminology Criteria for Adverse Events v4.03(CTCAE)The PI will determine the relationship of AEs to the test procedure/device/agent as not related, possibly related, probably related or definitely related, using standard criteria for clinical trials. Interim assessment of AEs will be conducted semi-annually by the data safety monitoring board.

Note: All serious adverse events will be followed until resolution of the events or definitive conclusion.

Hepatotoxicity

Administration of eltrombopag may cause hepatotoxicity. In the controlled clinical ITP studies, serum liver test abnormalities (predominantly Grade 2 or less in severity) were reported in 10% and 8% of the PROMACTA and placebo groups, respectively. Two patients (1%) treated with PROMACTA and two patients in the placebo group (3%) discontinued treatment due to hepatobiliary laboratory abnormalities. Seven of the patients treated with PROMACTA in the controlled studies with hepatobiliary laboratory abnormalities were re-exposed to PROMACTA in the extension study. Six of these patients again experienced liver test abnormalities (predominantly Grade 1) resulting in discontinuation of PROMACTA in one patient. In the extension study, one additional patient had PROMACTA discontinued due to liver test abnormalities (\leq Grade 3).

Serum ALT, AST, and bilirubin will be measured prior to initiation of PROMACTA, every 2 weeks during the dose adjustment phase and monthly following establishment of a stable dose. If bilirubin is elevated, perform fractionation. Evaluate abnormal serum liver tests with repeat testing within 3 to 5 days. If the abnormalities are confirmed, monitor serum liver tests weekly until the abnormality(ies) resolve, stabilize, or return to baseline levels. Discontinue PROMACTA if ALT levels increase to $\geq 3X$ the upper limit of normal (ULN) and are:

- Progressive, or
- Persistent for ≥ 4 weeks, or
- Accompanied by increased direct bilirubin, or

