History of Thromboembolic Events

Thrombotic events can occur at any platelet count. Thrombotic/thromboembolic complications may result from excessive increases in platelet counts. Excessive doses of eltrombopag or medication errors that result in excessive doses of eltrombopag may increase platelet counts to a level that produces thrombotic/thromboembolic complications. In the controlled ITP clinical studies, one thrombotic/thromboembolic complication was reported within the groups that received eltrombopag and none within the placebo groups. Seven patients experienced thrombotic/thromboembolic complications in the ITP extension study.

Caution should be used when administering eltrombopag to patients with known risk factors for thromboembolism (e.g., Factor V Leiden, ATIII deficiency, antiphospholipid syndrome, etc.).

Malignancies and Progression of Malignancies

Stimulation of the TPO receptor on the surface of hematopoietic cells by eltrombopag may increase the risk for hematologic malignancies. In the controlled ITP clinical studies, patients were treated with eltrombopag for a maximum of 6 weeks and during this period no hematologic malignancies were reported. One hematologic malignancy (non-Hodgkin's lymphoma) was reported in the ITP extension study.

Cataracts

Cataracts were observed in toxicology studies of eltrombopag in rodents (see Non-clinical Information). The clinical relevance of this finding continues to be evaluated in all ongoing NOVARTIS sponsored clinical studies. To date, there is however, no evidence that eltrombopag increases the incidence nor progression of cataracts in patients who have received eltrombopag. In the controlled ITP clinical studies, cataracts developed or worsened in five (5%) patients who received 50 mg eltrombopag daily and two (3%) placebo-group patients. In the ITP extension study, cataracts developed or worsened in 4% of patients who underwent ocular examination prior to therapy with eltrombopag. A significant proportion of patients in the ITP clinical studies were also exposed to chronic corticosteroid administration.

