6.4.6. Prompt Reporting of Serious Adverse Events and Other Events to NOVARTIS

Adverse events will be reported to the Investigational Review Board (IRB) as they occur and any

serious events will be reported to NOVARTIS within 24 hours of learning of the event if they occur. CTC criterion version 3.0 will be used as a guideline for reporting adverse events.

Any serious adverse events which occur during the clinical study or within 30 days of receiving the last dose of study medication, whether or not related to the study drug, must be reported by the investigator. In addition, any SAEs which occur as a result of protocol specific diagnostic procedures or interventions must also be reported.

All serious adverse events must be reported by facsimile or email within 24 hours to Novartis.

US CPO DS&E [contact]The SAE report should comprise a full written summary, detailing relevant aspects of the adverse events in question. Where applicable, information from relevant hospital case records and autopsy reports should be included. Follow-up information should be forwarded to NOVARTIS within 24 hours.

SAEs brought to the attention of the investigator at any time after cessation of eltrombopag and considered by the investigator to be related or possibly related to eltrombopag must be reported to NOVARTIS if and when they occur. Additionally, in order to fulfill international reporting obligations, SAEs that are related to study participation (e.g., procedures, invasive tests, change from existing therapy) or are related to a concurrent medication will be collected and recorded from the time the subject consents to participate in the study until he/she is discharged.

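### The Background section settles in advance that a first lymphoma is due to the disease, which conflicts with the protocol's own causality assessment and could affect reporting of a late case

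*Combined protocol and SAP*

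**What the plan says.** Section 1.1 gives the background risk: "There is an estimated 10% risk of malignancy, e.g. development of lymphoma, but this is not usually an early phenomenon". It applies this to the trial: "Perhaps 1-3 of the 15 patients in the study might be at risk for lymphoma over a lifetime". It then argues that a case is unlikely within a study it describes as fairly short, and adds: "If it were to happen in one patient, it would be attributed to the natural history of the disease". The sentence after that reads: "There would be no specific way to determine the etiology of any lymphoma that developed".

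Section 4.4 repeats the argument with a different count, "perhaps 2-3 of the 15 patients in the study might be at risk over a lifetime for a malignancy such as lymphoma", and the same appeal to a short study. The Schedule of Events runs to month 72.

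Section 6.3 takes another approach. The principal investigator "will determine the relationship of AEs to the test procedure/device/agent" in four grades, from not related to definitely related. The malignancy paragraph of the same section states: "Stimulation of the TPO receptor on the surface of hematopoietic cells by eltrombopag may increase the risk for hematologic malignancies". It also records one non-Hodgkin lymphoma in the ITP extension study.

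Section 6.4.6 requires every serious adverse event during the study, or within 30 days of the last dose, to be reported irrespective of causality. For events that come to light at any time after the drug is stopped, it says that those "considered by the investigator to be related or possibly related to eltrombopag must be reported to NOVARTIS if and when they occur".

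**The concern.** A causality assessment is informative only if its answer is open when the case arrives. Here it is closed for the first lymphoma, in a document that both concedes that etiology cannot be established and names a mechanism by which the drug could contribute. On those premises a judgement of possible relatedness has to remain available. The Background sentence takes it away from the person who must make the assessment.

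Two things are at stake. One is the relatedness grade for a first case, which matters more than usual because there is no concurrent control group to supply a comparison. The other is a late case: once the unconditional reporting period has passed, mandatory reporting to Novartis turns on the investigator's causality judgement, so a preset answer of natural history would take the event outside the requirement.

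**Working it through.** **1. The plan's own figure.** Inputs are 15 treated patients and a 10% malignancy risk, which the paragraph treats as a lifetime risk (section 1.1). Expected lifetime cases = 15 × 0.10 = 1.5. Under Binomial(15, 0.10), P(0) = 0.206, P(1) = 0.343, P(2) = 0.267 and P(3) = 0.129, so P(1 to 3) = 0.739. The range in section 1.1 is consistent with 10%. The range of 2 to 3 in section 4.4 has probability 0.395 and lies wholly above the mean of 1.5. The two sections should agree.

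**2. The statements side by side.**

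| Question | Section 1.1 | Section 6.3 |
|---|---|---|
| Can the cause of a lymphoma be determined? | No | Investigator grades each event by standard criteria |
| Could the drug contribute? | Not mentioned | Yes, for hematologic malignancies |
| Cause assigned to a single case | Natural history | Left to assessment |

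If the cause cannot be determined and a drug contribution is acknowledged, natural history cannot be the only permitted answer.

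**3. Where the attribution has an effect.**

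| Element | Depends on judged relatedness? |
|---|---|
| Relatedness grade of a first lymphoma (6.3) | Yes |
| Serious event during study or within 30 days of last dose (6.4.6) | No |
| Serious event after that (6.4.6) | Yes, for mandatory reporting to Novartis |
| Numbers of subjects with adverse and serious events (8.3.1.2) | No, not split by relatedness |
| Malignancy as a patient stopping rule (4.4.2) | No |
| Study stopping rules for malignancy (4.4, 4.4.1) | No, they count cases |
| Semi-annual monitoring board review (6.4.8) | No |

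Two rows depend on it. In the second of these, the event must fall more than 30 days after the last dose. If a patient off drug but still in follow-up counts as being in the study, it must also fall after the patient has left.

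**4. What one case could show.** The exact (Clopper-Pearson) 95% interval for 1 of 15 is 0.2% to 31.9%. A single case is compatible with the background risk and with a much higher one, so it supports neither attribution.

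**5. Illustration of how often a first case might arise on study.** The documents do not say over how many years the 10% accrues, so that period, L, is an assumption. Suppose a constant rate and all 15 patients followed for 6 years, giving 15 × 6 = 90 patient-years. Then the expected number = −ln(0.9)/L × 90, and P(at least one) = 1 − 0.9^(90/L). With per-patient risk q = 1 − 0.9^(6/L), P(exactly one) = 15q(1 − q)^14. For a doubled rate, 6/L becomes 12/L.

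| L (years) | Expected | P(≥1) | P(exactly 1) | P(≥2) | Rate doubled: P(exactly 1) | Rate doubled: P(≥2) |
|---|---|---|---|---|---|---|
| 20 | 0.47 | 0.378 | 0.300 | 0.078 | 0.379 | 0.233 |
| 40 | 0.24 | 0.211 | 0.189 | 0.023 | 0.300 | 0.078 |
| 70 | 0.14 | 0.127 | 0.119 | 0.008 | 0.209 | 0.029 |

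In every row exactly one case is more probable than two or more, at the background rate and at twice that rate. The outcome that the sentence covers is thus the likeliest non-zero outcome under either. The level of these probabilities is probably too high, because section 1.1 says malignancy is not usually early, most patients will be children, the 10% is not confined to lymphoma, and some patients will leave before year 6.

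**The case against.** The strongest reply is that the sentence is Background narrative and section 6.3 is operative. Nothing in section 1.1 instructs anyone to code an event as unrelated. A charitable reading is that one lymphoma cannot be told apart from background and so is not by itself a drug signal. That fits the study stopping rules, both of which tolerate one non-Hodgkin lymphoma but not two. The sentence also follows directly from remarks about the study period, so it most naturally concerns an on-study case, for which reporting is unconditional.

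Much of this stands. It confines the problem to the causality call and makes the late-reporting effect conditional on someone carrying the attribution forward. It does not rescue the wording. The sentence does not say that one case is uninformative; it assigns a cause, and the assessor named in section 6.3 works under the same protocol.

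Three stronger inferences are tempting and unsupported:

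- **That a first lymphoma would be tabulated as unrelated.** Section 8.3.1.2 does not split counts by relatedness, so the case is counted either way.
- **That the only route to a safety signal is removed.** Unconditional on-study reporting, count-based stopping rules, patient withdrawal and board review all operate without attribution.
- **That 13% to 38% is the chance of a case escaping reporting.** Those figures describe on-study time, when every serious event must be reported.

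**Conclusion.** The concern holds in a limited form. The protocol fixes the causality call for a first lymphoma, contrary to its own statement that etiology is indeterminable, its case-by-case assessment, and its acknowledged drug risk. The effect reaches that call and, conditionally, mandatory reporting to Novartis of a lymphoma found more than 30 days after the last dose. It does not fix the safety conclusion of the trial as a whole.

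This rests on comparing the text of sections 1.1, 6.3 and 6.4.6, and needs no assumed rate. The on-study probability of 13% to 38% is an illustration for assumed accrual periods of 70 down to 20 years, even accrual and complete six-year follow-up. It shows only that a single case is worth planning for. The description of the study as short does not sit with follow-up to month 72.

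**What to change.** - Delete the sentence in section 1.1 that assigns a single lymphoma to the disease.
- In sections 1.1 and 4.4, remove the argument from a short study or reconcile it with the schedule to month 72. Make the two lifetime counts (1 to 3 and 2 to 3 of 15) agree.
- In section 6.3, state that every malignancy is assessed case by case and is not coded as unrelated solely because the disease can cause it.
- In section 6.4.6, state that any malignancy the investigator learns of after the last dose is reported to Novartis, the IRB and the monitoring board, whatever its attributed cause. This applies to cases that come to the investigator's attention, so it adds no follow-up visits.

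An observed-against-expected analysis is not requested: it would need an age-specific background rate that the documents do not give. The cost is a few lines of text and at most a few extra reports, with no change to sample size, visits or analyses.

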1.2. Rationale

Eltrombopag has been remarkably efficacious in substantially increasing platelet counts in a high percentage of patients with chronic ITP (low platelets). The principal investigator [name] has been involved in various trials using eltrombopag; a recently published article detailing the success of eltrombopag illustrates the utility of this treatment (Gerrits et al, 2015). To greatly reduce or eliminate the risk of intracranial hemorrhage (ICH) in patients with WAS would be highly meaningful, as one of the five patients that we currently follow at our institution with XLT has already had an ICH; this is in keeping with published data. Even a relatively small increase in platelet count could be sufficient to prevent ICH in these patients. The ultimate purpose of providing

thrombopoietic treatment is to prevent serious, primarily intracranial, hemorrhage. Based on its utility in other diseases such as chronic ITP, thrombopoietic therapy appears to be the most promising approach for relieving the thrombocytopenia in WAS patients.

There is a very high rate of very serious bleeding associated with WAS and XLT patients (Ochs and Thrasher, 2006) that far exceeds that seen in almost any other form of childhood thrombocytopenia, including ITP (approximately 0.5%) (Kühne et al, 2003). We are targeting a pediatric population in the hopes of controlling and managing the excessive bleeding that occurs in a high percentage of patients with Wiskott Aldrich Syndrome including X-Linked Thrombocytopenia.

Preliminary analysis of 5 patients enrolled in this study along with 3 additional WAS/XLT patients (Gerrits et al, 2015) show that 5 of 8 WAS/XLT patients (3 XLT and 2 WAS) who were on eltrombopag treatment of at least 1 month (1 adult and 4 children) were platelet responders, as evidenced by achieving at least one platelet count $\geq 50 \times 10^9/L$ and double the baseline count. Six of 8 patients had reduced bleeding symptoms. Four eltrombopag-treated patients had platelet counts $\geq 20 \times 10^9/L$ above baseline counts and 4 patients reached counts $\geq 100 \times 10^9/L$.

2. OBJECTIVE(S)

2.1. Primary Objective

- To describe the pathophysiology of thrombocytopenia and bleeding in patients with Wiskott-Aldrich Syndrome (WAS) especially those with XLT (since they will be more stable and available for study) and determine their response to thrombopoietic agents *in vitro* and *in vivo*.

2.2. Secondary Objective

- This study aims to explore the functional state of circulating platelets in patients with WAS and to relate it to clinical bleeding. Furthermore to demonstrate whether a thrombopoietic agent, eltrombopag, administered daily will increase platelet production and platelet count, and reduce bleeding in patients with WAS.

3. INVESTIGATIONAL PLAN

3.1. Study Design

Fifteen patients (approximately 80% children) with WAS/ XLT will be enrolled and undergo baseline screening including not only blood drawing but also history of illness in the past, while ten additional WAS and XLT otherwise ineligible or unwilling patients who will not undergo study treatment and ten control subjects will undergo a one-time blood draw. The pediatric control and non-treatment WAS/XLT subjects will be pediatric patients who are having their blood drawn for reasons not related to an acute illness and will provide a limited amount of additional blood. The pediatric control and non-treatment WAS/XLT subjects will have their blood drawn at Cornell after giving consent. They will not be asked for more than 5-10 ml of blood per year of age up to a maximum of 30 ml total in one draw. Blood drawn will be studied for stem cells and

megakaryocytopoiesis, Immature Platelet Fraction (IPF), and platelet function (see table). These subjects will have their blood drawn for another purpose e.g. pre-op clearance for surgery and therefore it will be a small amount of extra blood posing a minimal risk to the subject. Subsequently, treatment patients will start on 2 mg/kg of eltrombopag and be seen every two weeks in the first month, and monthly for the first year. Although Promacta is commercially available in 25 mg and 50 mg tablets, it is also available for clinical studies in 12.5 mg tablets which will be provided by Novartis for this study. In this study, the starting dose will be based upon weight; patients over 50 kg will start at 50 mg daily unless they are of East Asian origin in which case they will use 25 mg as their initial dose. The dose of eltrombopag will be titrated for each subject based on their platelet response (see table 1). Overall, in this study, doses between 12.5mg every other day and 75mg once daily are anticipated to be required to maintain platelet counts between 50 and 400Gi/L. However, as explained in the provided dosing guidelines, the dose of eltrombopag will be reduced whenever the platelet count exceeds 200Gi/L in order to prevent it from reaching 400Gi/L. The goal is to have a platelet count in a safe hemostatic range, albeit not necessarily a normal platelet count.

Eltrombopag starting doses for children < 50kg will be scaled by body weight and the starting dose will be approximately 2 mg/kg once daily unless they are of East Asian origin in which case they will use approximately 1 mg/kg as their initial dose. This starting dose is based on the findings of GlaxoSmithKline's PETIT2 study: Eltrombopag for children with chronic immune thrombocytopenia (PETIT2): a randomised, multicentre, placebo-controlled trial.

This dosing schedule is based on those used in GlaxoSmithKline's 'PETIT' study: Eltrombopag in Pediatric patients with Thrombocytopenia from ITP.

For young children unable to swallow a tablet, eltrombopag powder for oral suspension (Eltrombopag PfOS) will be used. Each sachet contains eltrombopag equivalent to 20mg per gm of powder. Please see Appendix 3 for details and dose adjustment guidelines for subjects receiving the suspension formulation. Repeat assessment with the same testing will be performed at week 4. Dose adjustment will be based on the monthly monitoring of the platelet count.

The IPF will be measured at each visit with the CBC. Platelet count data will be collected throughout the study and used as part of the assessment of efficacy. Platelet count data will be collected as part of the CBC monthly during the first year of administration of study drug and at any dose change (eltrombopag or concomitant medication). If a subject continues on a stable dose during any stage of the study for greater than 4 weeks, a CBC (including platelet count) with differential will be performed no less frequently than every 4 weeks. Further information regarding reduction in use of concomitant medications for thrombocytopenia, use of rescue therapy, incidence and severity of bleeding and other symptoms associated with thrombocytopenia and infections will also be collected and summarized.

Platelet function will be assessed by whole blood flow cytometry as described by and in collaboration with [name] (see appendix for attached abstracts).

Treatment will be initiated at Cornell. Patients will be seen either at Cornell or by a their local doctor 1-3 months thereafter. A recently developed bleeding score, designed to incorporate the four leading bleeding scores, will be administered on study visits to semi-quantitatively assess bleeding.¹⁴ The Page bleeding score is completed using the information from this questionnaire. The hypothesis is that patients with Wiskott-Aldrich Syndrome will have more bleeding at given platelet counts than will patients with ITP. Furthermore the degree of bleeding will correlate not only with the platelet count but with the degree of platelet dysfunction. Platelet size will be explored also. We anticipate the platelet function and bleeding scores will improve with the institution of Promacta therapy if the

platelet counts increase. Even if some of these changes in bleeding are small, the overall direction will help to clarify the effect of treatment on these scores.

There is no placebo; thus, patients will be compared to themselves descriptively before and after treatment through complete physical examinations, complete blood draws, urinalysis, and platelet studies.

[name] has an appointment at Memorial Sloan Kettering, so a patient initiated at Cornell can be followed with appropriate testing at the MSKCC site. In addition, a patient who comes to the Cornell site to provide consent and initiate treatment may be followed at another site for local Laboratory Testing.

Urinalysis, Admission Panel (including liver tests), CBC with Platelet and Differential, PT/PTT, PFA, Fibrinogen, D-Dimers, Platelet Function Analysis, Immature Platelet Fraction (Platelet Reticulocyte Count), and Single Platelet Flow Cytometry will be assessed.

